Objective: This study aims to assess the levels of lens spoilage under standard wear and disinfection practices in order to determine the optimal lens replacement frequency of OK lenses. Further, this study will evaluate the health of anterior surface of the eye and lens comfort levels during one-year overnight use of OK lenses.

III. STUDY DESIGN

The proposed study uses a *prospective, observational quasi-experimental research design* where the contact lens spoilage from same participants will be observed over the time before and after contact lens wear. This design is well-suited for monitoring real-world lens wear and eye health outcomes. The term "quasi-experimental" suggests that the non-randomized, single group study, which is appropriate for this type of longitudinal observations studies.

Individuals (between 18 to 40 years of age) with a refractive error between -1.00 and -4.00D of sphere and astigmatism $\leq 2.50D$ will be recruited in the study. The eligible participants will receive study OK lenses during the dispensing visit, following the screening visit. Participants will attend total eight visits, including a follow up visit 2 weeks after the lens cessation which will

allow to assess the recovery or stabilization of eye surface measurements. At each visit, the anterior surface of the eye and comfort levels will be assessed using clinical microscope and by administering questionnaires. Further, lens fit assessment and care regimen compliance will be monitored closely. A photographic method will be used to qualitatively assess lens spoilage at each visit. Furthermore, during the lens dispensing visit, the 6-month visit, and the 1-year visit, lens deposition will be quantitatively evaluated using established standard laboratory procedures. This will allow us to investigate the long-term changes in the eye surface during the OK lens wear and to determine their association with eye discomfort. Additionally, the levels of lens spoilage at different time points and their association with eye discomfort will determine the optimal replacement schedule of OK lens.

Participants will be monitored for:

- Signs of eye surface changes (e.g., corneal staining, conjunctival health).
- Contact lens comfort measured using standardized surveys (e.g., OSDI, CLDEQ-8).
- Lens spoilage (e.g., surface scratches, protein deposition).

Outcomes:

- **Primary outcome:**
 - OK lens spoilage grading scores.
- **Secondary outcomes:**

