ii. **Qualitative assessment (On-eye):** After the lenses are worn by the participant, slit-lamp photographs will be captured to assess the lens surface quality (surface scratches and deposition) using the Zeiss SL 120 equipped with Cam Compact (Carl Zeiss Meditec AG, Jena).

iii. **Wettability assessment (On-eye):**

On-lens tear break-up time: In this test, participants will be asked to blink twice and hold the blink. Time from the last blink to the first random appearance of dry patch will be measured in seconds.

Fastness of dryness: The examiner will assess the fastness from the random appearance of dry patch to expand to the rest of the lens surface. Subjective grading – slow, medium and fast.

Grading of lens surface deposits and scratches:

- Surface deposits on the contact lens will be graded on a scale of 0 (absent, no deposits) to 4 (severe, deposits covering >75% of surface).
- Surface scratches
 - Extent: Front surface scratches (on eye) on the contact lens will be graded on a scale of 0 (absent, no scratches) to 4 (extensive, scratches covering >75% of surface).
 - Magnitude: Front surface scratches (on eye) on the contact lens were graded on a scale of 0 (absent, no scratches) to 4 (severe, very deep).

Contact lens comfort: Assessed by using Ocular Surface Disease Index (OSDI), the Contact Lens Dry Eye Questionnaire-8 (CLDEQ-8). The data obtained from this visit will serve as a baseline measurement.

After the lens surface assessment, participants will be trained on safe insertion and removal of OK lenses by the investigator. Once proficient, lens care procedures, including disinfection and storage, will be explained. Participants will be provided with contact lens care solutions. The details of contact lens care solutions are presented in **Table 2**. Participants will receive handouts detailing insertion, removal, and cleaning

instructions, along with an "**O-K Wear Time Journal**" to log lens use, bedtime, and wake times. Participants will be instructed to wear the lenses overnight for at least 6 hours. For after-hours support, contact details for the NSW Health Emergency Department will be provided in case of any unusual symptoms or issues.

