The study hypothesises that OK lens spoilage, including scratches and surface deposits, as well as eye discomfort levels, will progressively worsen across the visits at baseline visit, 6 months and 12 months visit. All the statistical methods will be aimed to address the given hypothesis.

Once all data are collected, different tests will be conducted to establish whether they follow normal distributions. This step will ensure us to choose the appropriate statistical test based on the data distribution. Continuous variables will be expressed as means \pm standard deviations, while categorical variable will be reported as medians and interquartile ranges (IQR). The time

effect (baseline, 6month and 12 month) and between-group differences in lens deposition levels, lens wettability scores, eye discomfort data from questionnaires, and eye surface changes will be tested with repeated measures ANOVAs (post-hoc tests) or Friedman test, with Bonferroni correction, where appropriate. This method will assess whether there are significant differences in spoilage across the three time points. If significant, post-hoc tests will help confirm if the worsening follows a progressive pattern from baseline visit to 12 months.

This study will use Spearman's correlation test to evaluate the correlations between the questionnaires scores (eye discomfort levels) and clinical test results (deposition and scratches). This correlation analysis will determine how these subjective and objective measures relate, further supporting the study hypothesis if a correlation is found. A value of $P < 0.05$ will be considered as significant. Furthermore, we determine to explore the association between OK lens replacement schedules and keratitis risk. By tracking lens spoilage, patient symptoms, and clinical indicators of infection over 12 months, we intend to gather preliminary data on infection risk. Given the difficulty of detecting keratitis with a small sample, we will use lens spoilage indicators as proxies for risk. We will also track all eye-related adverse events. While we may not establish a definitive keratitis rate, our approach will generate valuable insights on factors affecting OK lens-related health and guide future research on optimal replacement schedules to reduce keratitis risk.

VIII. STORAGE AND ARCHIVING OF STUDY DOCUMENTS.

Data format and storage location

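### Questionnaire-by-spoilage correlations are tested at an unadjusted P < 0.05, any one found is read as further support for the hypothesis, and the association helps to set the replacement schedule

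*Protocol*

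**What the plan says.** Protocol, section VII, Statistical Analysis, makes three linked statements about the correlations.

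- The method: "This study will use Spearman's correlation test to evaluate the correlations between the questionnaires scores (eye discomfort levels) and clinical test results (deposition and scratches").
- How a result will be read: "further supporting the study hypothesis if a correlation is found".
- The threshold, in the next sentence: "A value of $P < 0.05$ will be considered as significant".

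A multiplicity correction appears once, in the preceding paragraph, for the time-effect and group comparisons: "repeated measures ANOVAs (post-hoc tests) or Friedman test, with Bonferroni correction, where appropriate". Nothing ties it to the correlations. The section also says that all the statistical methods are directed at the hypothesis, which is that spoilage and discomfort worsen progressively from baseline through 6 to 12 months.

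Section III, Study Design, gives the association a further use: "the levels of lens spoilage at different time points and their association with eye discomfort will determine the optimal replacement schedule of OK lens".

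**The concern.** The protocol does not merely leave an adjustment unstated. It writes down how a result will be interpreted. No pair of variables, visit, direction, size or number of hits is required before a correlation counts in favour of the hypothesis. In a study of this size, several correlations each tested at 0.05 have a material chance of producing one small P value when nothing is there, and the wording would report that as support.

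The replacement schedule is the study's stated objective, and the same association is named as one of its two determinants. A chance finding could therefore reach the main recommendation.

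The clause also has a logical gap. The hypothesis is about change over time. A correlation between discomfort and spoilage across participants does not show that either has worsened, so even a true correlation would not establish what the clause says it supports.

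**Working it through.** The protocol gives no number of correlations and no family-wise error rate, so there is no stated figure to reproduce. The check builds a range from what the protocol lists.

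**Inputs from the protocol**

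- Threshold: 0.05, no adjustment tied to the correlations, sidedness not stated (Statistical Analysis).
- Questionnaires: two, OSDI and CLDEQ-8 (Detailed Study procedure, baseline visit).
- Spoilage grades: three, each 0 to 4, namely deposits, scratch extent and scratch magnitude (same place).
- Analysis time points: baseline, 6 and 12 months, stated for the time-effect tests and not for the correlations.
- Participants: 12 needed, 16 recruited (Sample size calculations).

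**Assumptions**

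- Every questionnaire is paired with every grade, with one value per person in each test. That gives 2 × 3 = 6 tests at one visit, 12 at two visits and 18 at three.
- Tests are two-sided.
- No true association exists between questionnaires and grades. Correlation among the questionnaires, among the grades, and across visits is varied from 0 to 0.8.

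**Step 1: independent tests as a benchmark.** For k independent tests, the chance of at least one P < 0.05 is 1 − 0.95^k. If only positive correlations count, each test contributes 0.025 and the chance is 1 − 0.975^k.

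| k | 1 − 0.95^k | 1 − 0.975^k |
|---|---|---|
| 6 | 0.265 | 0.141 |
| 12 | 0.460 | 0.262 |
| 18 | 0.603 | 0.366 |

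**Step 2: correlated measures.** Questionnaires, grades and visits will be correlated, which lowers these figures. Simulation with Spearman's coefficient and the t approximation, n = 12 and 16, gives these ranges as the assumed correlation goes from 0.8 (low end) to 0 (high end):

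| Tests | Any two-sided hit | Positive hit only |
|---|---|---|
| 6 (one visit) | 0.17-0.27 | 0.08-0.15 |
| 12 (two visits) | 0.28-0.49 | 0.14-0.28 |
| 18 (three visits) | 0.33-0.62 | 0.16-0.38 |

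The ends move by a few hundredths with simulation noise and with how correlation across visits is modelled. The high ends slightly exceed Step 1 for the same reason and because the t approximation is a little liberal at n = 12. Changing n between 12 and 16 makes little difference.

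**Step 3: compare with 0.05.** The lowest entry, 0.08, is 0.08 / 0.05 = 1.6 times the nominal level. The highest, 0.62, is about 12 times.

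**The case against.** Several points on the other side stand.

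- **The test family is inferred.** The protocol does not say that every pair is tested, at which visits, on which eye, or with scratch extent and magnitude kept apart. A reader might infer that every questionnaire-by-grade correlation will be tested, and that a chance supporting result is to be expected in a quarter to more than half of such trials. The text does not support stating that as fact. The rates are conditional on an assumed count and correlation.
- **Eighteen tests is the least plausible case.** It is the only one that exceeds one half. Baseline lenses are new, so their grades may lie at or near zero, and a grade that does not vary yields no coefficient.
- **Direction.** The hypothesis has both measures worsening, so more deposits with less discomfort could hardly be called support. Counting positive hits only roughly halves the rates, and no scenario then reaches one half. The protocol does not itself state a direction.
- **Weight.** The correlation is described as adding support, after the tests across time points. It is not a listed outcome. A reader might infer that it is confirmatory evidence, or that a significant P value by itself sets the schedule. Neither is written: the Study Design sentence names spoilage levels together with the association and gives no P-value rule.
- **Division of labour.** The number of secondary correlations and any adjustment are commonly left to a statistical analysis plan, which is not shown. Their absence is not the finding.

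What this does not answer is the interpretive clause. It is in the protocol, it sits beside a flat 0.05, and specifying the tests elsewhere would not make the clause sound.

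**Conclusion.** The point holds as a fault in a stated rule of interpretation. Reading any correlation found at an unadjusted 0.05 as support for the hypothesis gives a chance of false support above 0.05 in every scenario examined. For 6 to 12 tests it is about 0.17 to 0.49 if either direction counts, and about 0.08 to 0.28 if only positive correlations count. With 18 tests the figures are 0.33-0.62 and 0.16-0.38, but that case leans on baseline grades that may hardly vary.

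These figures rest on the assumed six pairs per visit, 12 to 16 participants, and correlations of 0 to 0.8 among the measures. None of them is a protocol figure. The analysis is secondary, so the consequence is an overstated conclusion and a weak input to the replacement recommendation. The tests across time points are not affected.

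**What to change.** In section VII, Statistical Analysis, delete the clause "further supporting the study hypothesis if a correlation is found" and state that the correlations are exploratory, reported as coefficients with 95% confidence intervals and without a significance claim. In section III, Study Design, describe the association between spoilage and discomfort as exploratory context for the replacement schedule, not as a determinant of it.

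If the sponsor wants one correlation to carry weight, the pair, visit and direction should be named in advance. The choice is the sponsor's. A multiplicity adjustment alone would not be enough: it needs a defined set of tests, and it would not close the gap between a correlation and a claim of worsening over time.

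The change is wording only, with no added visits, participants or measurements. The downside is that the correlations no longer count as support for the hypothesis.

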During the study, participants are required to wear OK lenses overnight and may experience possible temporary adherence of the contact lenses to the eye surface, mild irritation and discomfort due to lens edges rubbing against the eyelid margin, epithelial disruption or an allergic reaction to lens solution, mild discomfort, and a rare risk of corneal inflammation or infection.

Lens adherence is rare in open-eye rigid contact lens wear and is observed transiently on eye opening at a prevalence of about 80% after closed-eye rigid contact lens wear, where it may cause temporary localised corneal distortion and epithelial disruption. Previous research has demonstrated that these transient after-effects are rarely of clinical concern.

Epithelial disruption is a very common minor effect of wearing any contact lens, whether in research or clinical practice. The incidence of disruption varies considerably with wearing modality and lens type and is also patient-specific (for example, where there is underlying compromise of tear film or epithelial integrity prior to lens wear). Any such subjects will not be recruited for this research.

The risk of corneal inflammation and infection in short term soft and rigid contact lens wear are very low. Corneal infection is a rare disease in rigid contact lens wear and significantly lower than the risk posed by soft contact lens use. This slight risk is further reduced in this study because of the close clinical monitoring for warning signs and patient compliance, and the use of oxygen-permeable rigid lens materials appropriate for closed eye lens wear.

2. Likelihood and severity of complications:

The likelihood of developing corneal infections, including microbial keratitis, with orthokeratology (OK) lenses is relatively low, with an estimated incidence of 6.8 cases per 10,000 years of wear. This rate is lower than that associated with other overnight wear modalities of soft contact lenses. While the risk is rare, it cannot be classified as 'minimal' due to the potential for serious eye complications if an infection does occur. The severity of microbial keratitis can vary but may lead to significant discomfort, vision impairment, and, in severe cases, sight-threatening complications. This study aims to evaluate whether adjusting the lens replacement schedule can further mitigate this risk, enhancing the safety of OK lens wear for user.

3. Steps to minimise or prevent complications:

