The investigators are mindful of the need to actively reflect upon the balance between benefits and risks of a project while it is being conducted and the degree to which continuation of the study is justified should an adverse event be reported. Thus, any adverse event will be reported and handled in accordance with HREC Adverse Event Reporting Guidelines.

5. Benefits of the research outweigh the risk of harm or discomfort:

Eye infections associated with orthokeratology (OK) lenses is generally considered a low-incidence risk, particularly with proper lens care and adherence to recommended replacement schedules. While investigators cannot guarantee the direct benefits from this research, the potential benefits may include clear vision without needing to wear glasses or contact lenses during the day. The benefit of participating in this research study will contribute to the development of strategies that are aimed to minimise severe form of eye disease associated with long-term use of spoiled OK lenses.

Early Termination

The techniques proposed have been applied by the same and different investigators previously in multiple clinical studies and have not ever resulted in termination of any of these studies due to adverse events, so this is very unlikely. However, consideration for early termination of the study would occur if a serious adverse event is reported or if all collected data were of insufficient quality for analysis after repeated attempts at improving recording techniques and methods.

VII. STATISTICAL CONSIDERATIONS.

Sample size calculations

We are planning a study with an ordinal data response variable from matched pairs of study participants. We estimate that the difference in the lens spoilage grading between matched pairs is normally distributed with a standard deviation 0.9. To detect a true mean difference of 1.90 between pairs, we will need 12 subjects to achieve 80% power, assuming a Type I error rate of 0.05. To account for a 20% dropout rate, a total of 16 participants will be recruited. We will keep screening until we have met that target. However, since this sample size was not determined using the exact methodology relevant to the current study, we will collect pilot data as part of the research. Based on the pilot data results, we will recalculate the final sample size to ensure the statistical power is appropriately adjusted for the use of orthokeratology (OK) lenses.

Statistical Analysis

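### A single-schedule study of 16 people cannot link lens replacement to keratitis or select an optimal schedule, and the right lens at the 12-month visit is only about 6 months old

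*Protocol*

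**What the plan says.** Three claims concern replacement.

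- **Association with keratitis.** The Rationale (section I) and Statistical Analysis (section VII) both state: "we determine to explore the association between OK lens replacement schedules and keratitis risk".
- **Effect of changing the schedule.** Section VI.2, on likelihood and severity of complications, goes further: "This study aims to evaluate whether adjusting the lens replacement schedule can further mitigate this risk".
- **Optimal schedule.** The Summary and section II give the determination of the best replacement frequency as the purpose. Section III says that "the levels of lens spoilage at different time points and their association with eye discomfort will determine the optimal replacement schedule".

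The design behind these claims is a "non-randomized, single group study" (section III). Item 4 of the Detailed Study procedure gives every participant the same scheme. The right lens is taken for laboratory assay at 6 months and replaced by one of similar parameters. The left lens is assayed at 12 months, with no earlier exchange stated.

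Statistical Analysis plans a time effect over baseline, 6 and 12 months, between-group differences with no groups defined, and Spearman correlations of questionnaire scores with deposition and scratches. It also concedes that keratitis is hard to detect in a small sample, that spoilage will stand in for risk, and that a definitive rate may not be obtained.

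**The concern.** An association between two variables can be estimated only if both vary. Here the exposure (replacement schedule) is the same for every participant, and the outcome (keratitis) will almost certainly not occur. No listed analysis contains either variable. The stated aim is therefore out of reach of the design, whatever analysis plan is written later.

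The claim about an optimal schedule has a related weakness. A significant change over visits, with a correlation between spoilage and discomfort, shows that lenses deteriorate and that this may matter to wearers. It does not say at which age a lens should be replaced.

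The third issue affects a result the study will actually produce. Grades are analysed by visit, but visit and lens age part company in the right eye after month 6. If right-eye grades enter the 12-month time point, the hypothesised progression will be understated.

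**Working it through.** **Inputs.** "an estimated incidence of 6.8 cases per 10,000 years of wear" (section VI.2), that is 0.00068 per year; "a total of 16 participants will be recruited" (section VII), with 12 needed for analysis; follow-up from "clinical indicators of infection over 12 months" (section VII), taken as one year each. The protocol states no expected number of cases, so there is no figure to reproduce.

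**1. Expected cases and chance of any case.** Expected = N × 1 year × 0.00068; P(at least one) = 1 − exp(−expected).

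| Basis | Expected cases | P(at least one) |
|---|---|---|
| 16 participants | 16 × 0.00068 = 0.0109 | 1.1% |
| 12 completers | 12 × 0.00068 = 0.0082 | 0.8% |
| 32 eyes, if the rate is per eye | 32 × 0.00068 = 0.0218 | 2.2% |

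One expected case needs 1/0.00068 ≈ 1,471 years of wear.

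**2. What zero cases would show.** With 0 of 16, the exact two-sided 95% upper limit is 1 − 0.025^(1/16) = 20.6%. That is about 300 times the quoted yearly rate (0.206/0.00068 ≈ 303).

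**3. Variation in schedule.** Between participants there is none. Within a participant, the lens ages differ between eyes only after the exchange:

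| Visit | Right lens age | Left lens age |
|---|---|---|
| Baseline | 0 | 0 |
| 6 months (before exchange) | 6 months | 6 months |
| 12 months | about 6 months | 12 months |

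**4. Effect on the time analysis of grades.** Let G6 and G12 be the mean change in grade from baseline at lens ages 6 and 12 months. Assume the two eyes behave alike and the replacement lens ages like the original.

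- Left eye, 6-month to 12-month visit: G12 − G6.
- Right eye, same visits: G6 − G6 = 0.
- Both eyes averaged: (G6 + G12)/2 − G6 = (G12 − G6)/2, half the true change whatever the shape of the curve.

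From baseline to the 12-month visit, averaging the eyes shows (G6 + G12)/2. That lies between 50% of G12 (no change before 6 months) and 100% (no change after it).

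The protein assay is affected differently. It uses the right lens at baseline and 6 months and the left lens at 12 months, so lens age follows the visit but the eye changes.

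**5. Precision of a right-left comparison at 12 months.** For a two-sided paired t-test at 0.05 with 12 pairs and SD 0.9, 80% power corresponds to a difference of about 0.80 grade. The protocol does not say that its SD applies to fellow eyes, so this is an assumption. The detectable difference scales with the SD (0.80/0.9 ≈ 0.89 per unit of SD): about 0.53 grade at SD 0.6 and about 1.07 at SD 1.2.

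**The case against.** The strongest reply is that the protocol already admits the difficulty. Both places that announce the association go on to call the infection data preliminary, to offer spoilage as a proxy, and to speak of guiding future research. The Overview (section I) also gives a reason for the proxy: deposits can shelter microorganisms. This stands as far as event numbers go, and it would be unfair to say that the authors overlooked the problem. It does not answer the lack of variation in schedule. The proxy is unvalidated here, since nothing planned relates spoilage to infection, and section VI.2 makes its claim with no such caveat.

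Some stronger readings are tempting but not supported:

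- **That only 6- and 12-month lens ages are compared.** Baseline is in the planned test, and Table 3 schedules grading at 1, 7 and 21 days.
- **That the right-left comparison at 12 months is never analysed.** The undefined between-group differences might mean right versus left, and an analysis plan that is not shown might say so.
- **That the contrast between 6 and 12 months of lens age is lost.** The left lens is graded at both ages, and the planned post-hoc tests can cover it.
- **That the right-left comparison is a clean replacement experiment.** The right lens is the one exchanged in everyone, so lens age is fully confounded with eye side. Only the left lens is assayed at 12 months, and OSDI and CLDEQ-8 are not described as scored by eye.

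It is also fair to say that spoilage over time could support a replacement interval if a spoilage threshold were fixed in advance. The protocol rests the determination on levels over time and their association with discomfort, and those two alone do not select an interval.

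**Conclusion.** The point holds for three statements.

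1. The association of replacement schedule with keratitis, and the effect of adjusting the schedule, cannot be estimated. Schedule is constant between participants, and about 0.011 cases are expected (0.008 to 0.022 across the readings shown). This rests on the protocol's own incidence and one year of wear per participant.
2. The planned trend and correlation can describe spoilage but do not determine an optimal schedule.
3. The time effect by visit does not measure 12 months of lens wear in the right eye. If the eyes are averaged, the change from 6 to 12 months is halved under the assumptions stated. The protocol does not say how the eyes are combined, so the size of the distortion is conditional; the mismatch between visit and lens age is not.

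The description of spoilage itself remains a sound aim for this study.

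**What to change.** - Delete the schedule-keratitis association from the Rationale and from Statistical Analysis, and the claim about adjusting the schedule from section VI.2.
- Report keratitis and other eye adverse events as counts with exact intervals, so that zero cases in 16 is read beside its 20.6% upper limit.
- Restate the objective in the Summary and sections II and III as describing spoilage by lens age up to 12 months.
- Analyse deposit and scratch grades by lens age rather than by visit. Use the left, unexchanged lens for the trend over baseline, 6 and 12 months.
- Add, as a supportive analysis, the paired comparison at the 12-month visit of the right lens (about 6 months old) with the left lens (12 months old), with a 95% confidence interval. Cover deposit and scratch grades and staining by eye, and state that lens age is confounded with eye side.

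The cost is wording and a modest change of analysis on data already scheduled. The downside is a more modest claim. The added comparison gives no paired protein result and no comfort result by eye.
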